## **2.4 Primary Endpoints**

The ablated area on the radical prostatectomy specimen assessed by viability tissue staining (TTC).

## **2.5 Secondary Endpoints**

- The intra/post-operative safety of the targeted microwave ablation (number and severity of device- and procedure-related adverse events,
- TMA procedure duration: probe-in / probe-out time, ablation time
- Comparison between the ablation location in the prostate as seen in the KOELIS 3D map and the ablation location observed histologically on the prostatectomy specimen
- The change in urinary functions between baseline and each follow-up visit, using IPSS score and uroflowmetry
- The change in erectile functions between baseline and each follow-up visit, using IIEF-5 score
- The change in quality of life between baseline and each follow-up visit, using EPIC-26 score
- The correlation between the treatment effect dimensions measured histologically on the prostatectomy specimen resected after TMA, compared to the predictive ablation charts provided by the manufacturer
- The correlation between the treatment effect dimensions measured histologically on the prostatectomy specimen resected one month after TMA, compared to post TMA dimensions measured on the pre-RP mpMRI.
- Evaluation of the optimal treatment parameters to maximize the cell destruction without causing collateral damage.

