Diagnosis and Main Inclusion Criteria	
 
• Male
 
• Index lesion visible on multiparametric MRI confirmed by targeted transperineal biopsies using KOELIS Trinity®
 
• Having a diagnosis of prostate cancer (Gleason score ≤8)
 
• Prostate size ≤ 150 cc
 
• Patient suitable for IV sedation or general anesthesia and focal targeted microwave ablation
 
• Having elected to undergo RP as treatment of choice
 
• Ability to understand and the willingness to sign a written informed consent
 
• Free, informed, and written consent, dated and signed before the enrollment and before any exam required by the trial
 

Study Product(s), Dose, Route, Regimen	A TMA ablation will be performed during each intervention.
Duration of administration	NA
Reference therapy	NA
Statistical Methodology	
For practical considerations, the expected total number of study participants is 15 patients. This number may be extended in case further ablation parameters need to be tested.
 
An analysis is planned to determine TMA delivery protocol (number of ablations, energy output, and time needed to ablate one MRI-visible lesion).
 
We will assess the correlation between the treatment effect dimensions measured histologically on the prostatectomy specimen resected immediately or 1mo after targeted microwave ablation, compared to the predictive ablation charts provided by the manufacturer.
 
We will report the ablated area on the radical prostatectomy specimen assessed by viability tissue staining (TTC) on all fully evaluable patients.

---

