## 10.7 Data Analyses Plans

All patients who sign the consent form will be registered and entered the database. For each patient, we will list whether he received the assigned protocol (and if not, the reasons), the outcome of the procedures, compliance with the protocol (and reasons for failure to comply), adverse events with any of the procedures, MRI results, and targeted biopsy results.

- The data from the immediate resection phase and delayed resection phase will be separately evaluated. The observed ablated area in immediate resected prostatectomy specimen based on TTC staining will be compared with the predicted ablation area according to the template. The tissue viability will be evaluated by HE staining on delayed resection prostatectomy specimen.
- The comparison of the difference between the treatment effect dimensions measured histologically on the prostatectomy specimen resected after TMA and the predictive ablation charts provided by the manufacturer will be performed. For this analysis, the data from immediate resection phase and delayed resection phase are separately evaluated.
- The comparison between the treatment effect dimensions measured histologically on the prostatectomy specimen resected one month after TMA, compared to post TMA dimensions measured on the pre-RP mpMRI.
- To evaluate the intra/post-operative safety of TMA, we defined 30% as clinically acceptable severe adverse events (defined as CDC  $\geq 3$ ) rate. If the severe adverse events occur less than 30% (equivalent to less than 4 cases in 10 cases) for the delayed ablation phase, the feasibility of TMA is proved.

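### Chart and MRI predictability are labelled correlations, which cannot show systematic size error; Section 10.7 plans a difference for charts but names no measure of bias for MRI

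*Combined protocol and SAP*

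**What the plan says.** Section 2.5 lists two predictability endpoints among its nine secondary endpoints. For the manufacturer's charts it gives "The correlation between the treatment effect dimensions measured histologically on the prostatectomy specimen resected after TMA, compared to the predictive ablation charts". For imaging it gives "The correlation between the treatment effect dimensions measured histologically on the prostatectomy specimen resected one month after TMA, compared to post TMA dimensions", taken from the MRI done before prostatectomy. The secondary-endpoint list in the Study Summary words both the same way, and its Statistical Methodology entry repeats the chart version: "We will assess the correlation between the treatment effect dimensions measured histologically on the prostatectomy specimen".

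Section 10.7 never uses the word correlation.
- **Charts:** it plans "The comparison of the difference between the treatment effect dimensions measured histologically on the prostatectomy specimen resected after TMA and the predictive ablation charts", with the two phases evaluated separately. It also states that "The observed ablated area in immediate resected prostatectomy specimen based on TTC staining will be compared with the predicted ablation area according to the template".
- **MRI:** it has only "The comparison between the treatment effect dimensions measured histologically on the prostatectomy specimen resected one month after TMA", continued as "compared to post TMA dimensions measured on the pre-RP mpMRI". No difference, ratio or agreement statistic follows.

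No section names a coefficient, a mean difference, limits of agreement or a tolerance for either endpoint.

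**The concern.** The protocol's own questions are about accuracy. Section 1.3 asks whether the intended lesion mirrors the tissue actually destroyed, and whether MRI can confirm that treatment was complete. Section 1.6 asks how accurately the post-ablation MRI predicts the ablated dimensions. These questions concern agreement in centimetres. A correlation measures only whether larger predictions go with larger lesions.

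A systematic error is a realistic possibility. Section 4.2 says the chart dimensions come from other soft tissues, so a consistent shortfall or excess in prostate is what this trial is well placed to reveal. If the MRI endpoint were reported as the coefficient its definition suggests, MRI that misstated every zone by a constant factor could still be described as predictive.

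**Working it through.** The documents state no target correlation, tolerance, SD or power for these endpoints, so there is no figure of theirs to reproduce. The check asks what r and the mean difference each show when prediction is wrong by a known factor.

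**Inputs from Section 4.2.** Chart dimensions (short x long axis, cm) are 1.5 x 2.5, 2.0 x 2.7 and 2.5 x 3.0 for the short, medium and long ablation. Templates 1 and 2 place one ablation in each lobe; template 3 places one. The overlapped templates 4 and 5 are left out, because the readable text gives no predicted dimensions for them.
- Immediate phase, templates 1-3: 2 + 2 + 1 = 5 zones from three patients.
- Delayed phase, two patients per template: 4 + 4 + 2 = 10 zones from six patients.

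**Assumptions, not in the documents.** True size = k x chart + normal error, with SD 0.15 or 0.3 cm. Zones are treated as independent, although templates 1 and 2 put two in one patient.

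**Step 1: no error.** If y = kx with k > 0, then r = 1 for every k, while the mean difference is (k - 1) x mean chart size.
- Mean short axis: (1.5 + 1.5 + 2.0 + 2.0 + 2.5)/5 = 1.90 cm; delayed phase 19.0/10 = 1.90 cm.
- Mean long axis: (2.5 + 2.5 + 2.7 + 2.7 + 3.0)/5 = 2.68 cm; delayed phase 26.8/10 = 2.68 cm.

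CCC is Lin's concordance coefficient, which penalises bias.

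| k | r | Mean difference, short | Mean difference, long | CCC, short | CCC, long |
|---|---|---|---|---|---|
| 1.0 | 1.00 | 0 | 0 | 1.00 | 1.00 |
| 0.7 | 1.00 | -0.57 cm | -0.80 cm | 0.37 | 0.07 |
| 0.5 | 1.00 | -0.95 cm | -1.34 cm | 0.13 | 0.02 |

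**Step 2: with error.** Take k = 0.6. The mean difference is -0.4 x 1.90 = -0.76 cm (short) and -0.4 x 2.68 = -1.07 cm (long). In the chart's terms this is an over-prediction of 1/0.6 - 1 = 67%. Median r by simulation (second decimal good to about 0.01):

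| Case | Axis | Immediate | Delayed |
|---|---|---|---|
| 60% of chart, SD 0.15 | short | 0.91 | 0.87 |
| 60% of chart, SD 0.15 | long | 0.72 | 0.65 |
| 60% of chart, SD 0.3 | short | 0.73 | 0.65 |
| 60% of chart, SD 0.3 | long | 0.46 | 0.39 |
| Exact chart, SD 0.15 | short | 0.96 | 0.95 |
| Exact chart, SD 0.15 | long | 0.87 | 0.82 |

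At SD 0.15 cm, a chart whose zones come out 40% smaller than predicted scores higher on the short axis (0.91, 0.87) than an exactly right chart scores on the long axis (0.87, 0.82). The reason is the range of chart values: 1.0 cm on the short axis, 0.5 cm on the long.

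**Step 3: precision of r.** The Fisher interval is tanh(atanh r ± 1.96/√(n - 3)). For r = 0.9, atanh r = 1.472. At n = 5 the half-width is 1.386, giving 0.09 to 0.99. At n = 10 it is 0.741, giving 0.62 to 0.98.

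**Step 4: MRI.** The documents give no expected MRI dimensions, so no figure is offered. The algebra of Step 1 still applies: if histology were k times the MRI dimension, r without error would be 1 and the mean difference would be (k - 1) x mean MRI dimension. Only the second quantity shows the error, and Section 10.7 does not name it.

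**The case against.** **The analysis plan already covers charts.** Section 10.7 compares the difference between histology and chart, and compares the stained area with the predicted area in the immediate phase. Either would expose a systematic shortfall. This stands. A reader might infer from Section 2.5 that the trial cannot show whether the charts are right; Section 10.7 does not support that inference. For charts, what remains is a mismatch between endpoint and analysis and the lack of a named statistic.

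**No coefficient is named.** The protocol also uses the word correlation loosely. Section 9.1 carries it in its title and describes only specimen handling, and the endpoints themselves go on to speak of comparing. This stands in part. The loose reading leaves the MRI endpoint undefined instead of wrongly defined, and the remedy is the same.

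**A high r is not guaranteed.** A reader might infer that r will be high by design because the templates span several sizes. The tables above contradict this: r falls well below 0.9 on the long axis, or when noise is larger. The defensible statement is that r does not measure correctness in either direction.

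**Little depends on r.** These are two of nine secondary endpoints in a 15-patient feasibility study, and no decision rule uses them. Limits of agreement would also be imprecise. The standard error of a limit is about s√(1/n + 1.96²/(2(n - 1))), where s is the SD of the differences: √(0.100 + 0.213) = 0.56s at n = 10 and √(0.200 + 0.480) = 0.82s at n = 5. Both points stand. They limit how much weight the finding carries, but do not make correlation suitable for a question about accuracy.

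**Conclusion.** The point holds in a limited form. Section 2.5 and the Study Summary label both predictability endpoints as correlations although the stated questions concern accuracy, and a correlation cannot detect systematic over- or under-prediction. The substantive gap is MRI, where no section names a quantity that would show bias. For charts the fault is inconsistency, since Section 10.7 already plans a difference.

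The invariance of r to a constant factor is algebra and needs no assumption. The simulated values of r do rest on assumptions: the 60% factor, the noise SDs, independence of zones, and use of templates 1-3 only. They illustrate how r behaves and do not predict what the trial will find. The change should be made; it does not affect the primary endpoint.

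**What to change.** In Section 2.5 and the Study Summary, replace correlation with paired differences for both endpoints, in line with Section 10.7. In Section 10.7, state the same analysis explicitly for MRI.
- Report histology minus chart and histology minus MRI, and the corresponding ratios, per axis and by phase (MRI in the delayed phase only), with every zone listed.
- Give the mean difference with its 95% CI, and limits of agreement described as imprecise at these sample sizes.
- Allow for two ablations in one patient under templates 1 and 2.
- State which predicted dimensions the chart comparison uses for templates 4 and 5, or confine that comparison to templates 1-3.
- Keep r, if wanted, as a descriptive extra.

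The cost is a change of wording: the patients and measurements stay the same. The downside is that the results may look less favourable than a correlation would.

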## **2.6 Descriptive Endpoints**

NA

## **3.0 PATIENT ELIGIBILITY**

---

Eligibility waivers are not permitted. Subjects must meet the inclusion and exclusion criteria to be registered to the study. Study treatment may not begin until a subject is registered.

### **3.1 Inclusion Criteria**

- 3.1.1 Adult men diagnosed with prostate cancer and undergoing prostatectomy as treatment of choice
- 3.1.2 Index lesion visible on multiparametric MRI confirmed by targeted biopsies using KOELIS Trinity®
- 3.1.3 Patient suitable for IV sedation or general anesthesia and TMA
- 3.1.4 Free, informed, and written consent, dated and signed before the enrollment and before any exam required by the trial

### **3.2 Exclusion Criteria**

- 3.2.1 Past medical history of prostate surgery
- 3.2.2 Past medical history of radiotherapy or pelvic trauma
- 3.2.3 Past treatment for PCa (radiation, ablation, ADT, chemotherapy)

## **4.0 TREATMENT PLAN**

### **4.1 Treatment Dosage and Administration**

**Microwave:** Microwave radiation refers to the region of the electromagnetic spectrum with frequencies from 900 to 2450 MHz. Microwave can also be referred as “Ultra high radiofrequency” given the possible wavelength spectrum overlap. Water molecules have asymmetric electric charges. The alignment and the charges on the atoms are such that the hydrogen side has a positive charge, and the oxygen side has a negative charge. For a microwave oscillating at  $9.2 \times 10^8$  Hz, the charge changes signs nearly 2 billion times per second. When an oscillating electric charge interacts with a water molecule, it causes the molecule to flip. Microwave is specially tuned to the frequency of water molecules to maximize this interaction. As a result of the microwave radiation hitting the water molecules, the water molecule flips back and forth 2–5 billion times per second depending on the frequency of the microwave energy. The vigorous movement of water molecules raises the temperature which is a measure of how fast molecules move. Therefore, electromagnetic microwaves heat matter by agitating water molecules in the surrounding tissue, producing friction, raise temperature, and induce cellular death via coagulation necrosis]. This is one major difference between microwave that treat simultaneously a whole volume and other energies relying on radial conduction of the energy from the antenna (cryotherapy, radiofrequency).

We use MedWaves Avecure generator and associated microwave antenna, used for thermal microwave ablation. Under general anesthesia and ultrasound guidance, the prostate is visualized, and the optimal approach is determined. A thin (16-gauge) microwave antenna is then placed directly into the targeted area. When the antenna is attached to the microwave generator with a coaxial cable, an electromagnetic microwave is emitted from the noninsulated portion of the antenna. The

---

generator produces 10-60W of power at a frequency of 902-928 MHz. Intratissue temperatures can be measured with built-in temperature sensor [33].

**MRI/US fusion and OBT-Fusion®: Targeted Microwave Ablation (TMA)** is the specific wording when microwave is combined with an MRI/US fusion guidance system, the latter providing improved planning, guiding and visualization capabilities compared with conventional ultrasound systems. During the trial the KOELIS Trinity® system will be used. This 510k-cleared medical device embeds four key technologies that are relevant for focal therapy using microwave:

- 3D Ultrasound using motorized ultrasound probes that allow to reconstruct the prostate in 3D in a few seconds with no probe movement. The ultrasound probe comes with guiding accessories (needle guides) to offer improved guidance of the diagnostic or therapeutic instrument in the prostate
- Elastic MRI/US fusion allowing to precisely fuse a preoperative MRI containing relevant tumor information (location, size, aggressiveness) with intraoperative 3D Ultrasound to allow the physician to guide the needles directly inside the index tumor. This technology is necessary given that direct in-bore MRI guidance is cost and time consuming.
- OBT-Fusion® is an image-based tracking technology that tracks and helps navigate the needle inside the prostate during the whole intervention. A patented algorithm then recognizes the needle location in a reference 3D ultrasound volume acquired at the beginning of the exam. The advantages are an increased accuracy due to the automatic patient and prostate movement during the exam, an absence of need of further sensors that are usually required to have such navigation capability, and an automatic recalibration throughout the exam instead of manual recalibration
- 2nd Look is a specific KOELIS technology that allows to recall the biopsy mapping information during a second intervention, which can typically be a focal treatment. The recalled information include the number of targeted and systematic cores, the location of MRI lesions that were biopsied, the histological features of each individual cores. The key advantage is the ability to further personalize the treatment plan according to each patient, rather than relying only on the MRI information.

[name] who is an image-guided focal therapy expert will be delivering the TMA ablation for all the interventions[39]–[42].

#### 4.2 Toxicities and Dosing Delays/Dose Modifications

We will monitor for TMA related toxicities such as rectal injury, bladder injury, and perineal pain. Complications will be managed with best supportive care. Since previous literatures have not adapted similar study design (TMA and immediately resect), we do not have standard dosage of TMA needed to ablate planned area on the prostate. Therefore, we start from low output and ablation time and escalate them in accordance with corresponding histologically ablated area.

---

According to the manufacturer's data based on other soft tissues, ablation coverages of short x long axis (cm) are estimated 1.5 x 2.5 for short-time (3min) ablation, 2.0 x 2.7 for medium-time (5min) ablation, and 2.5 x 3.0 for long-time ablation.

Based on the data, our TMA delivery strategy is planned as follows.

### **Immediate resection phase**

1st patient

#### **Template #1**

Right lobe: Single Small (3min) Ablation  
Left lobe: Single Small (3min) Ablation

2nd patient

#### **Template #2**

Right lobe: Single Medium (5min) Ablation  
Left lobe: Single Medium (5min) Ablation

3rd patient

#### **Template #3**

Single lobe: Single Large (7.5min) Ablation

4th patient

#### **Template #4**

Single lobe: Spatially-overlapped Double Medium-time (5min) Ablation

5th patient

#### **Template #5**

Single lobe: Spatially-overlapped Double Large (7.5min) Ablation

### **Delayed resection phase**

6-7th patient

#### **Template #1**

8-9th patient

#### **Template #2**

10-11th patient

#### **Template #3**

12-13th patient

#### **Template #4**

14-15th patient

#### **Template #5**

In order to avoid collateral damage and for safety, the TMA delivery protocol may be modified by the physician's discretion but still in accordance with the manufacturer's recommendation.

### **4.3 Concomitant Medications/Treatments**

NA.

---

#### **4.4 Other Modalities or Procedures**

##### **4.4.1 Radical prostatectomy**

First 5 patients undergo RP immediately after TMA under the same anesthesia as their definitive treatment for PCa.

Following 10 patients undergo RP one month after TMA under the general anesthesia as their definitive treatment for PCa. This surgery is performed as standard of care.

##### **4.4.2 Duration of Therapy**

One session (one entire TMA procedure consisting of one to two ablations in accordance with TMA delivery protocol) only.

#### **4.5 Removal of Patients from Protocol Therapy**

Patients can be taken off the study treatment and/or study at any time at their own request, or they may be withdrawn at the discretion of the investigator for safety, behavioral or administrative reasons. The reason(s) for discontinuation of treatment will be documented and may include:

- Patient withdraws consent
- Patient is unable to comply with protocol requirements
- Patient experiences toxicity that makes continuation in the protocol unsafe
- Treating physician determines continuation on the study would not be in the patient's best interest

Notify the Principal Investigator and document the reason for study removal and the date the patient was removed from treatment in the Case Report Form. The patient should be followed-up with per protocol.

#### **4.6 Duration of Follow Up**

The study will begin at the time of informed consent and ends at 30 days ( $\pm$  15 days) visit following RP. No further follow-up is required as part of this study.

#### **4.7 Patient Replacement**

Patients may be removed from the study at any time either via patient preference or failing to undergo either TMA or RP. If a patient is removed from the study, an additional patient may be enrolled. Patients who complete all procedures outlined in this protocol will be considered "fully evaluable", whereas those who fail to undergo any of the procedures (i.e. TMA or RP) will be considered "not fully evaluable". We will report the numbers and percent of men considered "not evaluable". If there are more than 1 or 2, we will try to figure out if there are any salient characteristics that distinguish "fully evaluable" from "not fully evaluable" patients.

### **5.0 STUDY PROCEDURES**

#### **5.1 Screening Phase and Baseline Procedures**

Assessments performed exclusively to determine eligibility for this study will be done during initial clinical visit. It is acceptable to allow assessments performed

---

per standard clinical indications to be used for baseline values, but these again should be done within the screening window of 90 days or need to be repeated.

The screening procedures include:

**Routine procedures done for patient's medical care:**

**5.1.1 Medical history**

Complete medical and surgical history.

**5.1.2 Demographics**

Age

**5.1.3 Review subject eligibility criteria**

**5.1.4 Review previous and concomitant medications**

**5.1.5 Physical exam and standard perioperative blood tests**

Vital signs (temperature, pulse, respirations, blood pressure), height, weight. Bloods include full blood count, renal function and coagulation profile, tumor markers.

